6.1 Investigational treatment

The terms “investigational study drug(s)” or “study drug(s)” will refer to oral RUXOLITINIB (also known as INCB18424) tablets and oral PANOBINOSTAT (also known as LBH589) capsules and both drugs will be supplied by Incyte and Novartis, respectively, at no cost to the subjects.

6.1.1 Dosing administration

RUXOLITINIB is administered orally BID everyday in a 28-day treatment cycle (Q4wk). Induction phase dose is 10 mg PO BID. In the combination phase, the starting dose of RUXOLITINIB is 10 mg and may be increased to 15mg PO BID. See [Table 6-1](#), [Table 6-2](#) for dose and treatment schedules.

PANOBINOSTAT is administered orally TIW, QOW, or QW in a 28-day cycle depending on the assigned cohort. Starting dose of PANOBINOSTAT is 10mg TIW QOW and may be increased to 20mg TIW QW depending on the assigned cohort. See [Table 6-1](#) for dose and treatment schedules.

Patients may take RUXOLITINIB and PANOBINOSTAT without regard to food. However, once the patient has made a choice (e.g., take drug after breakfast or at fasting), it is recommended that patient will follow the election choice consistently throughout the protocol.

On Day -28, the first dose of RUXOLITINIB only will be administered at the clinical site. First dose of PANOBINOSTAT will start on Cycle 1 Day 1 administered with the RUXOLITINIB morning dose at the clinical site. See [Table 6-2](#) for provisional escalating dose levels.

Table 6-1 Dose and treatment schedule

Study treatments	Pharmaceutical form and route of administration	Escalating Doses	Frequency and/or Regimen
RUXOLITINIB	Oral	10,15 mg	Twice daily, 28-day cycles
PANOBINOSTAT	Oral	10, 15 mg	Three times a week, every other week, 28-day cycles OR Three times a week, every week, 28 day cycle To be taken with the AM dose of RUXOLITINIB

Patients will self-administer RUXOLITINIB and PANOBINOSTAT as instructed as follows:

- RUXOLITINIB will be orally administered BID (approximately 12 hours apart: morning and evening)
- PANOBINOSTAT should be taken orally TIW (e.g. day 1, 3, and 5) at the same time on each day with the AM dose of RUXOLITINIB. Doses should be separated by a minimum of 30 hours within the week of dosing

- Dose may be taken with or without food
- Each dose of study drug should be taken with a glass of non-carbonated water (approximately 8 ounces/240ml). Patients should be instructed to swallow the capsules/tablets whole and not chew them.
- Patients must avoid grapefruits, grapefruit juice, pomegranate, starfruit, starfruit juice, Seville oranges and Seville orange juice during the entire study treatment period
- The timing of the clinic visit for ECG monitoring (7-1) should be considered when determining the initial time of dosing, as the dose time on the day of ECG performance should be consistent, as much as possible, throughout the study.
- If the patient forgets to take a dose of RUXOLITINIB, then he/she should take study drug within 3 hours after the missed dose. If more than 3 hours have passed, then that missed dose should be omitted and the patients should continue treatment with the next scheduled dose.
- If the patient forgets to take a dose of PANOBINOSTAT, then he/she should take study drug within 12 hours after the missed dose. If more than 12 hours have passed, then that missed dose should be omitted and the patients should continue treatment with the next scheduled dose.
- If a patient vomits study drug within one hour of study drug administration, the dose will not be re-administered. The patient will resume therapy at the next scheduled dose. On all other days corresponding to study visits, the patients may take the morning dose of study drug prior to their scheduled clinic visit.
- If vomiting occurs on non-study visit days, re-dosing of the patient is not allowed before the next scheduled dose, and the event should be noted in the appropriate eCRFs.

6.1.2 Ancillary treatments

Not applicable

6.1.3 Rescue medication

Not applicable

6.1.4 Guidelines for continuation of treatment

Patients may continue treatment until they progress, withdraw consent, experience unacceptable toxicity, start new MF therapy, and/or it is believed by the investigator to be in the best interest of the patient to discontinue (in consultation between the sponsor and investigator).

6.1.5 Study duration

The study will continue until the last patient completes all required safety evaluations per protocol per extension stage of Phase II protocol.

6.2 Dose escalation guidelines

6.2.1 Starting dose rationale

In [CLBH589BUS32T], the established MTD of PANOBINOSTAT in patients with MF, was 25mg PO TIW QW. PANOBINOSTAT has been tolerated up to a dose of 80mg TIW QW, but the majority of these patients will dose reduce due to toxicities [CLBH589B2102]. RUXOLITINIB has been tolerated up to doses of 50mg BID, but a minimum of 25% reduction in splenomegaly was seen in the majority of patients treated at 10mg BID, 15mg BID, and 25mg BID (Verstovsek 2010). From [INCB018424-251], 15mg BID was established as the most effective and safest starting dose, followed by individualized dose titration (Verstovsek 2010).

As described in Section 2.4, there was synergistic anti-proliferative activity seen in a preclinical *in vitro* experiment (Wang 2009) when combining the JAK2 inhibitor TG101209 and PANOBINOSTAT. This combination of agents was effective in attenuating mutant JAK2V617F, p-STAT3 and p-STAT5, especially when PANOBINOSTAT was combined with lower concentrations of TG101209.

In the interest of patient safety, both of these compounds will start at dose levels below 50% of the respective maximum tolerated doses due to the potential overlapping toxicity with respect to thrombocytopenia, anemia and neutropenia. This was also determined to be an appropriate way to assess if a more biologically effective dose could be found prior to determining the MTD for this combination. As such the provisional doses are shown in Table 6-2.

6.2.2 Provisional dose levels

The provisional dose escalation levels for RUXOLITINIB and PANOBINOSTAT are described in Table 6-2. Deviation from this provisional dose escalation plan is allowed if emerging data on toxicities and signals for activity are observed and are felt to be important to warrant modification of the provisional dose levels by the Investigators. It will be the responsibility of the Investigators to provide appropriate rationale and study data to justify deviation. Any planned deviation from the provisional dose escalation levels shown in Table 6.2 will have to first be approved by the local IRB, FDA and Novartis.

Table 6-2 Dose escalation cohorts for combination therapy evaluable phase I study

		Cohorts							
		1	2	3	4a	4b	5	6	7
RUXOLITINIB	10mg	10mg	10mg	15mg	15mg	15mg	15mg	15mg	15mg
	PO	PO	PO	PO	PO	PO	PO	PO	PO
	BID	BID	BID	BID	BID	BID	BID	BID	BID
PANOBINOSTAT	10mg	15mg	20mg	15mg*	20	10mg	15mg	20mg	
	PO	PO	PO	PO	mg	PO	PO	PO	
	TIW	TIW	TIW	TIW	PO	TIW	TIW	TIW	
	QOW	QOW	QOW	QOW	TIW	QW	QW	QW	
Cumulative dose/cycle	60mg	90mg	120mg	90mg*	120mg	120mg	180mg	240mg	

*DOSE WILL DEPEND ON PREVIOUS COHORT AND WILL EITHER BE PANOBINOSTAT 10MG, 15MG OR 20MG PO TIW QOW FOR A CUMULATIVE DOSE/CYCLE OF EITHER 60MG, 90MG, OR 120MG

6.2.3 Criteria for dose escalation and determination of MTD and/or RPTD

A patient will be considered evaluable for the dose-determining set if he or she experiences a DLT during the combination phase days 1 to 28, or is observed for at least 28 days in the combination phase and is fully evaluated for any toxicities and has completed all study required tests. Patients who do not experience a DLT in the 28 days of the combination phase are considered evaluable if they have taken at least 50% of the RUXOLITINIB doses and not missed more than 1 dose of PANOBINOSTAT in the QOW dosing cohorts and no more than 2 doses in the QW dosing cohorts.

All available safety information (including DLTs, adverse events that are not DLTs, vital signs, and ECGs will be reviewed by the investigators in each cohort to decide if the next dose cohort will begin. Drug administration at the next dose level may not proceed until the investigators have documented it is safe to proceed to a higher dose level. Dose escalation will continue until identification of the MTD and/or RPTD is made.

The initial 3 cohorts will have RUXOLITINIB administered at a fixed dose of 10mg PO BID and cohort 1 will combine PANOBINOSTAT at a dose of 10mg PO TIW QOW, cohort 2 will be PANOBINOSTAT 15mg PO TIW QOW and cohort 3 will be PANOBINOSTAT 20mg PO TIW QOW for cumulative cycle doses of 60mg, 90mg and 120mg, respectively. If an MTD of PANOBINOSTAT is not established by cohort 3, then cohort 4a will test RUXOLITINIB at 15mg PO BID in combination with PANOBINOSTAT 15mg PO TIW QOW and 20mg PO TIW QOW in 4b. If an MTD of PANOBINOSTAT is established in the first 3 cohorts, then the cohort 4a will test RUXOLITINIB at 15mg PO BID in combination with PANOBINOSTAT at the dose level preceding the MTD dose level of PANOBINOSTAT.

If the dose escalation of RUXOLITINIB continues to cohort 4b and this cohort does not define the MTD of RUXOLITINIB, then cohort 5 will allow patients to be treated at a dose of PANOBINOSTAT of 10mg PO TIW QW for a cumulative dose/cycle of 120mg. Cohorts 6 and 7 will be pursued if the previous cohorts don't reach MTD and will include 15mg PO BID of RUXOLITINIB and 15mg PO TIW QW and 20mg PO TIW QW, respectively.

The RPTD of each agent will be determined by the MTD and the dose limiting toxicities observed in Phase I. The RPTD will not necessarily be the MTD doses reached in the Phase I dose escalation part of this study. However, the RPTD will not exceed the estimated MTD dose of either drug as determined from the drugs given in combination in Phase I. The decision to define the RPTD will ultimately be made by the PI and will be based on the toxicity profiles and in part any and all data on tolerability and efficacy of the combination therapy in the Phase I patients who remain on study drugs beyond the first cycle.

6.2.3.1 Definition of MTD

The MTD is defined as the highest drug dosage not causing in the first cycle of treatment medically unacceptable, dose-limiting toxicity in more than 33% of the treated patients.

6.2.3.2 Definition of RPTD

If the evolving safety profile (long term or overall) along with other assessments suggest that further increases in dose will result in excessive toxicity, without substantial benefit in exposure/activity, the dose escalation phase of the study will be halted. The potential RPTD will be determined by a combination of the MTD determination in the Phase I and the tolerability and efficacy of PANOBINOSTAT and RUXOLITINIB in combination over multiple cycles in patients who remain receiving therapy beyond cycle 1. The rationale for this approach is based on the fact that although higher doses of PANOBINOSTAT may be tolerated, lower doses (or alterations in the treatment schedule) may be equally effective or even more effective in inducing chromatin modifying effects in the malignant cells while limiting both heme and non-heme toxicities. It is the hypothesis of the investigators based on the previous studies of PANOBINOSTAT in MF that lower doses of drug delivered over extended periods of time are most effective and most well tolerated.

6.2.4 Dose cohort modification

Provisional dose level cohorts are listed in Table 6-2. Possible changes in dose administration include but are not limited to:

- Expansion of the current dose group to further assess safety
- Administration of an intermediate dose between the current and preceding dose
- Administration of an intermediate dose between the current and the next planned dose
- Termination of any further escalation of study drug

If there is less than the required number of evaluable patients, then additional patients will be enrolled until at least the minimum number of evaluable patients is available for assessment.

6.2.5 Definitions of dose limiting toxicities (DLTs)

DLTs are listed in Table 6-3, and will be defined as all AEs of the specified grade occurring within Days 1-28 of the combination phase, unless clearly and incontrovertibly due to extraneous causes.. Table 6-3 was created using Common Terminology Criteria for Adverse Events (CTCAE) v4.03.

For the purpose of dose-escalation decisions, only DLTs occurring during the first 28 days of treatment with RUXOLITINIB and PANOBINOSTAT will be considered and included in dose escalation decisions. However, all safety information including adverse events, ECG monitoring data, and vital sign abnormalities, will be included in the final decision for dose escalation and determination of how many patients should be evaluated at a given dose level.

Thrombocytopenia will only be considered a DLT in the combination phase (Day 1-28) if the platelet count is recorded below 10,000/ μ l by manual count or $\geq 10,000/\mu\text{l}$ and associated with a grade 3 bleed. Phase I patients who require platelet transfusions within Days 1-28 will have to be removed from study. Patients are allowed to receive platelet transfusions after day 28 if clinically warranted, and this does not necessitate removal from study. Transfusional support of red blood cells (RBC) is permissible at any point in the study and is not considered a DLT.

In the event that an AE begins during the first 28 days of combination therapy, but does not qualify for the definition of a DLT at the time of the dose-escalation decision, due to a specific length requirement until Cycle 2; it will be provisionally considered a DLT during the decision-making process. Adverse events occurring after treatment day 28 will not be considered DLTs, however, they will guide the decision of dose escalation and how many patients will be evaluated at a given dose level. All AE's, vital signs, and ECG data will be included in the final analysis to determine the MTD and/or RPTD.

Table 6-3 Criteria for Defining Dose Limiting Toxicity (DLT)

TOXICITY	Any of the following criteria:
Hematologic	
Febrile Neutropenia	≥Grade 3 (ANC < 1.0 x 10 ⁹ /L + Fever single reading >38.3°C or ≥38°C sustained >1 hr)
Thrombocytopenia	<10 x 10 ⁹ /ul or ≥10 x 10 ⁹ /ul associated with grade 3 bleeding
Non-Hematologic	
Gastrointestinal	
Vomiting	≥Grade 3
Nausea	≥Grade 3 nausea uncontrolled despite use of standard anti-emetics
Diarrhea	≥Grade 3 Diarrhea
Constitutional symptoms	
Fatigue	Grade 4 Fatigue
Hepatobiliary	
Bilirubin	≥Grade 3, Coincident Direct Bilirubin ≥0.5mg/dl
AST/SGOT and/or ALT/SGPT	≥ Grade 3
	≥Grade 4
Other	
Any Grade 3 non-hematologic toxicity : With the exception of: ≥Grade 3 QTc prolongation (QTc > 500 ms), which is a DLT at any incidence	
Any Grade 4 non-hematologic toxicity	

Any of the following AEs, which when assessed as treatment related, will require patients to be permanently discontinued from study:

- any grade ≥ 3 hemorrhagic event
- 2nd episode of grade ≥ 3 febrile neutropenia
- grade 3 renal toxicity
- grade ≥ 3 QTc prolongation (QTc > 500 ms)
- grade 4 renal toxicity
- grade 4 serum bilirubin with direct bilirubin ≥ 0.5 mg/dL
- grade 4 non-hematologic toxicity

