6.2.8 Dose modifications for prolonged QTc interval

All cardiac events should be treated as per the local standard of care and referred to a specialist if clinically indicated. Any final decision concerning dose modifications or permanent discontinuation of the patient from study drug due to QTc prolongation will be based on the assessment of the Investigator. If a patient cannot be dosed due to prolonged QTc for more than 7 days since last dose, the patient should be discontinued from study. See Table 6-4 for further details on criteria for dose delays, dose reductions, and re-initiation of study treatment for drug related QTc abnormalities.

Table 6-4 Criteria for dose delays, dose reductions, and re-initiation of treatment due to study drug related QTc abnormalities*

ECGs to be performed at specified time point	Abnormality Noted	Dose Modification Guideline - At any time during a cycle of therapy (including intended day of dosing)
Pre-Dose Combination phase day 1 (triplicate ECGs only)		
Pre-dose in cycle 1, Day 1 : 3 ECGs separated by 5-10 minutes, obtained prior to dosing	One of the three ECGs obtained shows QTc > 500 msec	Check and correct the patient's serum potassium, magnesium and calcium immediately, as well as evaluate con-meds.. Delay PANOBINOSTAT dose at least 3 days and repeat ECGs in triplicate. If the 3 ECGs: QTc > 500 msec, discontinue patient from study.
Post-Dose Combination phase day 1 and Subsequent Cycles (triplicate ECG only)		
3 hr Post-Dose: triplicate ECGs Cycle 1, Day 1, 5, 8, 15, 22 Cycle 2 Day 1 (Day 29) and beyond	One of the three ECGs obtained shows QTc > 500 msec OR QTc increased > 60 msec compared to baseline.	Check and correct the patient's serum potassium, magnesium and calcium immediately, as well as evaluate con-meds. Monitor ECG hourly or by telemetry until at least 2 consecutive hourly ECGs performed at least 3 hours post dose are <500. If any ECG has QTc > 500 msec. discontinue patient from study.

* If there are no additional procedures to be carried out on the day, arrangements may be made such that the ECGs may be performed at their local physician's office near the patient's home and transmitted to the site investigator or responsible delegate in a timely manner. ECGs done outside the MSSM MPD clinic are only permitted day 29 and beyond.

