7.2.5 Laboratory evaluations

The laboratory evaluations will be performed by a local lab according to the visit schedule in Appendix 2 (+/- 3 days up until the end of cycle 6 and then +/- 7 days for C7 and beyond).

Abnormal laboratory values or test results constitute as an AE only if they induce clinical signs or symptoms, and are considered clinically significant (i.e., require dose modification and/or interruption of study drug, lead to clinical symptoms, cause study discontinuation or constitute in and of itself an SAE) or require therapy. These events should be recorded on the eCRF. If the administration of PANOBINOSTAT and/or RUXOLITINIB is delayed/modified due to unacceptable toxicities (see Section 6.2.7), re-evaluation should be performed prior to the next study treatment at a minimum.

All available labs should be performed and results of Hematology reviewed prior to administration of study drug. More frequent examinations may be performed at the Investigator's discretion if medically indicated; results should be recorded on the Unscheduled Visit eCRF.

Baseline labs may be repeated, if needed, to obtain acceptable values before the patient would screen fail. Laboratory tests should be collected and analyzed on the scheduled day appendix 2, or +/- 3 days up until the end of cycle 6 and then +/- 7 days for C7 and beyond.

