* CTD³ may also be CTD for patients that will continue on the extension stage of the study.

³ Each study visit from cycle -1 to EOS has a +/- 3 day window. End of study visit should be at least 30 days after patient stops taking study medications.

*** these tests will be performed when clinically indicated and not on each visit and not more frequently than every 6 months

 RESEARCH RELATED
 STANDARD OF CARE

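### The DLT window closes on Day 28, but the legible schedules go from Day 22 to Day 29 +/- 3 days, so an asymptomatic Cycle 1 event first found by test at that visit enters the 3+3 count or not according to the appointment date

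*Combined protocol and SAP*

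**What the plan says.** **DLT window.** Section 6.2.5 limits the escalation count to Days 1-28 of combination therapy: "only DLTs occurring during the first 28 days of treatment with RUXOLITINIB and PANOBINOSTAT will be considered and included in dose escalation decisions". Later events are handled separately: "Adverse events occurring after treatment day 28 will not be considered DLTs, however, they will guide the decision of dose escalation".

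**Test-based DLTs.** For platelets the date of the draw decides: "Thrombocytopenia will only be considered a DLT in the combination phase (Day 1-28) if the platelet count is recorded below 10,000"/ul, or a higher count with a grade 3 bleed. QTc above 500 ms is in Table 6-3 as a toxicity "which is a DLT at any incidence". Neither has a duration requirement.

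**Schedule.** Table 7-1 lists Cycle 1 ECGs on Days 1, 4, 8, 15 and 22. Table 6-4 also ends Cycle 1 at Day 22 and continues with "Cycle 2 Day 1 (Day 29) and beyond". The legible Appendix 2 grid, which is the Phase 2 one, has Cycle 1 columns at Days 1, 4, 8, 15 and 22 and then Day 29.

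**Visit windows.** Section 7.2.5: "Laboratory tests should be collected and analyzed on the scheduled day appendix 2, or +/- 3 days up until the end of cycle 6". Appendix 2: "Each study visit from cycle -1 to EOS has a +/- 3 day window".

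**What the count drives.** Section 6.2.3.1 defines the MTD by dose-limiting toxicity in the first cycle. Section 10.4.2.1 turns the number of DLTs among 3 or 6 patients into the escalation decision.

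**The concern.** Section 1.4.2 expects thrombocytopenia to be the dose-limiting toxicity of this combination. Without bleeding, a platelet count below the DLT limit is found only by a blood draw. On the schedules that can be read, the first draw after Day 22 is nominally on Day 29, one day after the window closes.

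Section 7.2.5 asks for haematology to be reviewed before study drug is given. A pre-dose Cycle 2 Day 1 result therefore reflects Cycle 1 panobinostat only. By the MTD definition it is first-cycle information, yet the DLT rule leaves it out unless the visit happens to be early.

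At stake is a count of 0, 1 or 2 events among three to six patients, where one event can change the decision. The site sets the visit date, the investigators make the escalation decision (6.2.3), and there is no data monitoring committee (8.6).

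**Working it through.** **1. Visit date against the window.** Day 29 +/- 3 gives Days 26 to 32.
- Days 26, 27, 28 (3 of 7 possible dates): a first-detected platelet count below 10,000/ul or QTc above 500 ms is a DLT.
- Days 29, 30, 31, 32 (4 of 7, including the nominal date): the same finding is not a DLT.

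**2. The uncovered stretch.** On nominal dates, Days 23-28 have no scheduled check: 6/28 = 21% of the window. The Day 22 visit may itself fall on Days 19-25, so the stretch from that visit to Day 28 runs from 3 to 9 days.

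**3. Which cohorts.** Section 6.1.1 gives days 1, 3 and 5 as an example of the three-times-weekly pattern.
- Weekly cohorts 5-7: week-4 doses fall on about Days 22, 24 and 26. That is 3 of 12 doses per cycle, with no scheduled in-window check after the last two, or after the first if the Day 22 tests are pre-dose as in Table 7-1.
- Every-other-week cohorts 1-4b: if dosing is in weeks 1 and 3, the last dose is on about Day 19, and the Day 22 visit follows all Cycle 1 panobinostat.

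**4. The plan's own operating characteristics (10.8).** With true DLT rate p,

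P(escalate) = (1-p)^3 + 3p(1-p)^2 x (1-p)^3.

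- p = 0.30: 0.343 + 0.441 x 0.343 = 0.494 (plan: .49)
- p = 0.40: 0.216 + 0.432 x 0.216 = 0.309 (plan: .31)

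All 14 entries of the table reproduce to rounding, so the table assumes that every true DLT is counted.

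**5. If a share m of true DLTs is not counted.** The counted rate is p(1-m), put into the same formula. The documents give no value for m; both values below are assumptions.

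| True rate p | m = 0 | m = 10% | m = 6/28 = 21% |
|---|---|---|---|
| 0.30 | 0.494 | 0.557 (counted rate 0.270) | 0.631 (0.236) |
| 0.40 | 0.309 | 0.378 (0.360) | 0.465 (0.314) |

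The 21% column is the ceiling under a constant hazard on nominal visit dates: every event arising on Days 23-28 goes uncounted, including symptomatic ones that would in fact be dated by onset.

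**6. Does another rule catch these events?** The provisional-DLT sentence in 6.2.5 covers events that began by Day 28 and await a duration criterion; the platelet and QTc criteria have none. Evaluability in 6.2.3 requires 28 observed days and all required tests, but names no end-of-window test. A visit on Day 26 or 27 also precedes completion of those 28 days.

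**The case against.** **The Phase 1 grid is unreadable.** Section 7.2.5 sends laboratory timing to Appendix 2, and the Phase 1 grid there did not survive text extraction. A Day 28 blood count cannot be ruled out. This stands: the platelet part is conditional on a check by the sponsor. The ECG part rests on Table 7-1 and is not conditional.

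**Late findings are not ignored.** A reader who stops at "Adverse events occurring after treatment day 28 will not be considered DLTs" might infer that a Day 29 platelet count is disregarded. The documents do not support that. The same sentence lets later events guide escalation, 6.2.5 brings all safety information into the final decision, 6.2.3 bars the next level until the investigators document that it is safe, and 6.2.4 allows expansion, an intermediate dose or an end to escalation. Section 7.2.5 permits extra tests, and a platelet transfusion on Days 1-28 is itself a DLT (4.1). These soften the effect, but none changes the formal count that 10.4.2.1 uses.

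**Most DLTs are symptomatic.** Vomiting, diarrhoea, fatigue, febrile neutropenia and bleeding can be dated by onset. This stands and limits the point to test-detected events.

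**A quarter of DLTs is not lost.** Because 3 of 12 weekly doses fall on or after Day 22, one might infer that 25% of DLTs go uncounted. A share of doses is not a share of events, and 25% exceeds the 21% constant-hazard figure. Table 2-1 gives a median time to grade 3/4 thrombocytopenia of 12 days on weekly dosing, although in Hodgkin patients at higher doses.

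**Little QTc signal is lost at Day 29.** From a last weekly dose on about Day 26 to a pre-dose Day 29 ECG is about 72 hours. With the 15-18 hour half-life in 1.2.4, that is 72/18 = 4.0 to 72/15 = 4.8 half-lives. This stands; platelets are the main issue.

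**Conclusion.** The concern holds in a limited form and is of moderate severity. As written, the same asymptomatic, test-detected Cycle 1 event is or is not a DLT depending on whether the Cycle 2 Day 1 visit falls on Days 26-28 or Days 29-32. Where such an event goes uncounted, the bias is toward escalation. It matters most in cohorts 5-7, which are reached only if cohort 4b does not define the MTD.

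The size is unknown. The 10% and 21% rows are illustrations that treat the 3+3 rule as mechanical, without the investigators' discretion, and should not be read as estimates of missed toxicity. The conclusion on platelets assumes that Phase 1 blood draws follow the same Cycle 1 days as Table 7-1 and the Phase 2 grid. If the Phase 1 grid has a Day 28 count, that part largely falls away, provided the +/- 3 day window cannot move that draw past Day 28.

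**What to change.** First, confirm from the Phase 1 grid in Appendix 2 whether a blood count is scheduled on Day 28.

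If not, state in 6.2.5 and 6.2.3 that, for the escalation count and the dose-determining set:
- the DLT evaluation runs from Cycle 1 Day 1 through the pre-dose Cycle 2 Day 1 assessments;
- these are done no earlier than completion of Day 28;
- their results are required before a patient without a DLT is counted as evaluable.

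The passages on removal from study, platelet transfusion and dose modification switch at Day 28/29 (4.1, 6.2.5, 6.2.7 and Table 6.2.3). A Day 29-32 finding that counts as a DLT would otherwise fall under both sets of rules. They must be reconciled with the new definition; which clinical rule should apply is for the investigators and is not proposed here.

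Cost: an amendment that touches several sections, with no new visit or test and no change in sample size. The cohort decision may wait up to about 4 days (Day 32 instead of Day 28), and a few more events may count.
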